Aims & Endpoints	
Among women with VBD-p and VBD-c, determine the efficacy of peripheral, central, and combined treatments in:
 
Aim 1. Alleviating pain Primary Endpoints: Ia. pain score during tampon test at 16 weeks Ib. self-reported pain via SF-MPQ at 16 weeks Secondary Endpoints: IIa. experimental pain via local and remote PPTs at 16 weeks IIb. COPC pain levels via COPC follow-up survey at 16 weeks IIc. Pain scores and PPTs at 8 weeks and 24 weeks
 
Aim 2. Improving patient reported outcomes Primary Endpoints: Ia. self-reported physical/mental health via SF12v2 at 16 weeks Ib. sexual health via PROMIS at 16 weeks Secondary Endpoints: IIa. mood via SCL-27 at 16 weeks IIb. somatic awareness via PILL at 16 weeks

- IIc. perceived stress *via* PSS at 16 weeks
- IId. sleep *via* sleep scale at 16 weeks
- IIE. Patient reported outcomes at 8 weeks and 24 weeks

Aim 3. Normalizing cytokine and microRNA expression

Primary Endpoints:

- Ia. cytokine levels *via* mesoscale discovery assays at 16 weeks
- Ib. microRNA levels *via* sequencing read at 16 weeks

Secondary Endpoints:

- IIa. cytokine and microRNA levels at 8 weeks and 24 weeks
- IIb. Aim 3 will also identify cytokine and microRNA biomarkers at baseline that predict treatment response at 8, 16, and 24 weeks

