5 BASIC STUDY DESIGN

Vestibulodynia UPDATE is a multi-center, randomized, double-blind, placebo-controlled trial designed to determine the efficacy of peripheral lidocaine/estradiol cream, centrally-targeted nortriptyline pills, and combined treatments compared to matching placebo with the primary endpoints of change in pain, self-reported health, and cytokine/microRNA measures at 16 weeks and secondary endpoints of change in these measures at 8 weeks and 24 weeks.

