12 OUTCOME DETERMINATIONS

Aim 1. Determine the efficacy of peripheral, central, and combined treatments in alleviating pain among women with VBD-p and VBD-c.

Primary Endpoints:

- Ia. pain score during tampon test at 16 weeks
- Ib. self-reported pain *via* SF-MPQ at 16 weeks

Secondary Endpoints:

- Ila. experimental pain *via* local and remote PPTs at 16 weeks
- Ilb. COPC pain levels *via* COPC follow-up survey at 16 weeks
- Ilc. Pain scores and PPTs at 8 weeks and 24 weeks

Aim 2. Determine the efficacy of peripheral, central, and combined treatments in improving patient reported outcomes among women with VBD-p and VBD-c.

Primary Endpoints:

- Ia. self-reported physical/mental health *via* SF12v2 at 16 weeks
- Ib. sexual health *via* PROMIS at 16 weeks

Secondary Endpoints:

- Ila. mood *via* SCL-27 at 16 weeks
- Ilb. somatic awareness *via* PILL at 16 weeks
- Ilc. perceived stress *via* PSS at 16 weeks
- Ild. sleep *via* sleep scale at 16 weeks
- Ile. Patient reported outcomes at 8 weeks and 24 weeks

Aim 3. Determine the efficacy of peripheral, central, and combined treatments in normalizing cytokine and microRNA expression profiles in vaginal and blood tissues collected from women with VBD-p and VBD-c.

Primary Endpoints:

- Ia. cytokine levels *via* mesoscale discovery assays at 16 weeks
- Ib. microRNA levels *via* sequencing read at 16 weeks

Secondary Endpoints:

- Ila. cytokine and microRNA levels at 8 weeks and 24 weeks
- Ilb. Aim 3 will also identify cytokine and microRNA biomarkers at baseline that predict treatment response at 8, 16, and 24 weeks

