To answer question 2a, we will fit three linear regression models with the dependent continuous variable being a variable for each of the 3 patient reported outcomes (SF12 physical health score, SF12 mental health score, and PROMIS sexual health score). VBD subtype will be the predictor of interest. Covariates will include age (continuous variable), race (coded as in model 1a), study site. Regression coefficient for VBD subtype will be tested for statistical significance using Bonferroni-corrected threshold alpha 0.0166 (corrected for 3 tests corresponding to 3 outcomes). Regression coefficient significance will suggest outcomes differ by VBD subtype.

To answer question 2b, three MMRM models analogous to model 2b will be fit, where Y is a continuous variable representing the primary outcomes measured at 16 weeks. Similar to 2b, we will jointly evaluate the significance of additional interaction terms using an F-test (“overall test”). Significant F-test will suggest that the effect of either nortriptyline or lidocaine/estradiol cream, or both, differ by VBD subtype. In this case, we will compare the LS means of the treatment differences in each treatment-VBD-subtype subgroup, after appropriate Bonferroni correction. Secondary outcomes will also include change in SCL-27 mood score, PILL somatization score, and PROMIS biopsychosocial trait scores from baseline to 16 weeks following treatment. Secondary outcomes also include change in patient-reported outcomes from baseline to the 8-week time point and change in pain scores and PPTs from the 16-week to the 24-week time point.

Expected Outcomes. **1)** For women with VBD-p, peripheral lidocaine/estradiol treatment will be more effective than placebo or nortriptyline in improving perceived physical, mental, and sexual health at 8 and 16 weeks. **2)** For women with VBD-c, centrally-targeted nortriptyline treatment will be more effective than placebo or lidocaine/estradiol in improving perceived physical, mental, and sexual health at 16 weeks. **3)** For women with VBD-c, combined peripheral and centrally-targeted treatments will be most effective in improving health at 16 weeks. **4)** The two VBD subtypes will exhibit differential responses to treatment withdrawal, such that women with VBD-c report decreases in perceived health from 16 to 24 weeks compared to women with VBD-p.

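### Aims 1 and 2: Section 15.3 assigns pain variables to the Aim 2 week-24 outcome, and neither aim pre-specifies a treatment difference at week 24

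*Combined protocol and SAP*

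**What the plan says.** **Endpoint lists.** The Executive Summary gives the Aim 1 secondary endpoint as "IIc. Pain scores and PPTs at 8 weeks and 24 weeks". Section 12 gives the Aim 2 counterpart, IIe, as "Patient reported outcomes at 8 weeks and 24 weeks". Both lists treat weeks 8 and 24 in parallel and name no reference visit. Section 5 speaks of "secondary endpoints of change in these measures at 8 weeks and 24 weeks", also without a reference visit.

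**Analysis text, Aim 1 (Section 15.2).** Week-8 pain scores and PPTs are analysed as change from baseline. Week-24 pain scores and PPTs are analysed as change from week 16.

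**Analysis text, Aim 2 (Section 15.3).** The week-8 outcome is "change in patient-reported outcomes from baseline to the 8-week time point". The outcome that follows it for week 24 is "change in pain scores and PPTs from the 16-week to the 24-week time point". The models for question 2b are described as ones "where Y is a continuous variable representing the primary outcomes measured at 16 weeks". Expected Outcome 4 in the same section predicts that "women with VBD-c report decreases in perceived health from 16 to 24 weeks compared to women with VBD-p".

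**Timing.** Under Section 8.1 the cream ends at week 16 and the pill is tapered over weeks 16 to 18. Week 24 is therefore the only off-treatment visit.

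**The concern.** There are two separate problems.

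In Aim 2 the variables are wrong. An analyst who follows Section 15.3 literally would analyse pain scores and PPTs again. Endpoint IIe at week 24 and the perceived-health hypothesis would have no planned analysis.

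In Aim 1 the variables are right, but the only week-24 outcome is measured from the point where treatment stops. Such a change shows what was lost. It does not show what benefit remains. It also depends on how much each group gained first, so a subtype that improved more on treatment has more to lose. Expected Outcome 4 (more worsening in VBD-c after withdrawal) could appear to hold for that reason alone.

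Section 3.1 cites limited follow-up data as a weakness of earlier trials, and week 24 is where this trial could address it. If the week-24 comparison is chosen only after results are known, it loses the protection of pre-specification.

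**Working it through.** **Text comparison, Aim 2.** The list requires patient-reported outcomes at weeks 8 and 24. Section 15.3 supplies them for week 8 and substitutes pain scores and PPTs for week 24, in the words used for Aim 1 in Section 15.2. No other sentence in 15.3 fills the gap, because the question 2b models are written for week-16 outcomes. The questionnaires themselves are scheduled at week 24 (Section 11.3, Appendix A). What is missing is the analysis, and the data exist.

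**Text comparison, Aim 1.** The model for question 1a in Section 15.2 takes the longitudinal tampon score with visit and treatment-by-visit terms. It does not say which visits enter, and it names no week-24 contrast. Differences from placebo are estimated only if the overall F-test is significant. For PPTs, the 16-to-24 change is the only week-24 outcome named.

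**What the 16-to-24 change measures.** Let d be the benefit over placebo at week 16 and r the fraction kept at week 24. In the direction of benefit:

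- benefit at week 24 = d × r
- 16-to-24 contrast against placebo = d × r − d = −d × (1 − r)

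The plan gives no week-24 figure, so d is borrowed from Section 15.6, which states 0.98 points as the detectable difference for one arm against placebo at alpha 0.0167.

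| Case | Benefit at week 24 | 16-to-24 contrast |
|---|---|---|
| Inert arm (d = 0) | 0 | 0 |
| d = 0.98, all kept (r = 1) | 0.98 | 0 |
| d = 0.98, half kept (r = 0.5) | 0.49 | −0.49 |
| d = 0.98, none kept (r = 0) | 0 | −0.98 |

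The first two rows cannot be told apart by the 16-to-24 contrast.

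**Dependence on prior gain.** Suppose one subtype gains 0.98 and the other 0.49, and both keep half. The losses are 0.98 × 0.5 = 0.49 and 0.49 × 0.5 = 0.245. The subtypes differ by 0.245 in withdrawal change although they retain the same fraction.

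**Power illustration.** Inputs from Sections 5.3 and 15.6: 400 women allocated 1:1:1:1 with 20% attrition, so 80 per arm; SD 2.0; within-subject correlation 0.5. Tests are assumed two-sided.

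- SD of a change = 2.0 × √(2 × (1 − 0.5)) = 2.0
- standard error = 2.0 × √(2/80) = 0.316
- check of the plan's 0.98 at power 0.80: (2.393 + 0.842) × 0.316 = 1.02 with 80 per arm, and 0.92 with 100 per arm. The stated figure lies between these; nothing below depends on reproducing it.
- all benefit kept, baseline-to-24 contrast: 0.98/0.316 = 3.099; power = Φ(3.099 − 1.960) = 0.873 at alpha 0.05, and Φ(3.099 − 2.393) = 0.760 at alpha 0.0167
- all benefit kept, 16-to-24 contrast: expected value 0, so it rejects only at the alpha level
- half kept: both contrasts have size 0.49, and power is 0.341 or 0.199
- none kept: the two contrasts exchange roles

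With a correlation of 0.3 to 0.7, the 0.873 becomes 0.745 to 0.979 and the 0.760 becomes 0.589 to 0.946.

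**The case against.** The 16-to-24 change answers a question that the plan asks. Expected Outcome 4 in both 15.2 and 15.3 concerns the response to treatment withdrawal, and change since withdrawal is a legitimate estimand for it. No expected outcome for Aims 1 or 2 claims durable benefit. Section 15 says that secondary outcomes also include this change, which does not withdraw the list in Section 12. The Aim 2 wording is probably a drafting slip: the same paragraph uses patient-reported outcomes for week 8, and it refers question 2b to its own model. All of this stands, and it is why the 16-to-24 change should be kept.

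A reader might infer that durable benefit cannot be shown at all. The documents do not support that. The baseline-to-24 effect is the sum of the baseline-to-16 and 16-to-24 effects, and the longitudinal tampon-score model would yield a week-24 difference if week 24 is among its visits. A reader might also extend the point to every week-24 endpoint, but Section 15.4 evaluates biomarkers at 0, 8, 16 and 24 weeks. Nor does Section 5 conflict with a change endpoint, since it speaks of change without naming a reference.

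The objection does not reach two things. No analysis of patient-reported outcomes at week 24 is specified, and no week-24 difference from placebo is pre-specified for Aims 1 or 2. The tampon-score model does not cover PPTs or patient-reported outcomes, and its visits are unnamed.

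**Conclusion.** The point holds for Aims 1 and 2 only.

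- **Aim 2.** Section 15.3 names the wrong variables for week 24. Endpoint IIe at that visit and Expected Outcome 4 have no specified analysis. This rests on the text alone.
- **Aim 1.** The one named week-24 outcome suits the withdrawal hypothesis but cannot by itself separate fully kept benefit from no benefit, and no week-24 contrast is pre-specified.

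The algebra holds for any d and r. The 0.98-point example is an illustration on the 0–10 pain scale. It is not a week-24 figure from the plan and does not carry over to PPTs, SF-12 or PROMIS. The power figures assume 80 per arm, SD 2.0 and correlation 0.5. These are secondary endpoints, so the primary week-16 comparisons are unaffected. The change should still be made before the analysis is fixed.

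**What to change.** 1. In Section 15.3, replace pain scores and PPTs with the patient-reported outcomes. This alone is not enough, because it would leave week 16 as the only reference.
2. In both 15.2 and 15.3, pre-specify the active-minus-placebo difference at week 24, baseline-referenced, overall and by subtype. Take it from a longitudinal MMRM that includes week 24: the existing model for the tampon score, and analogous models for SF-MPQ, PPTs and patient-reported outcomes. Name the visits in each model, and state whether the week-24 contrast depends on the overall F-test.
3. Keep the 16-to-24 change as the withdrawal estimand, and report it beside the week-16 effect so that loss is read against gain.

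The cost is protocol and SAP wording, a few additional model fits, and more secondary contrasts to report. No new data are needed for the tampon test, PPTs or questionnaires that Appendix A schedules at week 24. Appendix A does not list SF-MPQ by name, although Section 4 plans the McGill questionnaire at week 24, so its collection should be confirmed.

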15.4 Analysis of the Aim 3 Endpoints

Cytokine Expression levels will be measured in vaginal lavage samples and plasma isolated from whole blood. We will use a standard Human MesoScale Discovery multiplex kit to measure 36 inflammatory mediators (4 tier-1 and 32 tier-2).

Tier-1 mediators include the pro-inflammatory cytokines IL-1 β ,⁵⁹⁻⁶¹ IL-8,^{7,60,62} and IL-17⁶³ and anti-inflammatory cytokine IL-1ra.^{7,61} These cytokines were selected based on previous associations with VBD case status and symptom severity.

Tier-2 mediators include cytokines (e.g., interleukin 6; IL-6), chemokines (e.g., monocyte chemoattractant protein 1; MCP1), and growth factors (e.g., vascular endothelial growth factor; VEGF) that are involved in peripheral and central sensitization, inflammation, and chronic pain.¹²⁸

miRNA Expression levels will be measured in vaginal swab samples and blood. We will isolate total RNA and then ship the RNA to UT Health Genome Sequencing Facility (GSF), directed by [name]. The GSF core will perform small RNA library preparation and sequencing.

Data Analysis. The two primary statistical questions for Aim 3 are: 3a) At baseline, is there an inverse association between VBD 'centralness' score (determined by the number of COPC sites) and the levels of Tier-1 cytokines in vaginal samples; and a positive association between VBD 'centralness' score and the levels of Tier-1 cytokines in plasma samples? 3b) Do biomarkers in vaginal fluid predict response to peripheral treatment and biomarkers in blood predict response to central treatment?

To answer question 3a, we will fit a linear regression model where cytokine level (skewed variables will be transformed (e.g., log, box-cox) to approximate normal distribution) will be a continuous dependent variable and VBD 'centralness' score, will be the main predictor of interest. Covariates will include age and race. Significance of regression coefficient associated with the 'centralness' score will be evaluated using an F-test and significance threshold (alpha) Bonferroni-corrected for the number of cytokines assessed (4 cytokines corresponding to 4 statistical tests). Subgroup means, mean differences and 95% confidence intervals will be output.

To answer question 3b, we will fit a MMRM model analogous to 1a, with additional terms of treatment cytokine (in blood and vaginal samples) interaction, visit cytokine interaction, and treatment visit cytokine interaction. Significance of additional interaction terms will be evaluated using an F-test. Significant ($p < 0.05$) F-test will suggest that treatment effects by nortriptyline or lidocaine/estradiol cream or both, are modified by cytokines.

Secondary analyses for Aim 3 will include the association of Tier 2 biomarkers (cytokines and miRNAs) with VBD subtype and interaction with treatment response. These analyses will be analogous to those specified for questions 3a and 3b, with p-value thresholds kept at 0.05 due to exploratory nature of these analyses. In our secondary analyses we will also evaluate the change of biomarker concentrations (blood and vaginal samples) over time (at 0, 8, 16, and 24 weeks) in each treatment group and VBD subtype. We hypothesize that these biomarkers may serve as intermediate phenotypes for treatment success in VBD patient subgroups.

Expected Outcomes. 1) Women with VBD-p will have higher levels of inflammatory mediators in peripheral vaginal samples, while women with VBD-c will have higher levels of inflammatory mediators in circulating blood measured at the baseline visit (0 weeks). 2) Abnormalities in baseline vaginal cytokine and miRNA biomarkers will predict a positive response to peripheral lidocaine/estradiol treatment, while abnormalities in blood biomarkers will predict a positive response to centrally-targeted nortriptyline or combined treatment. 3) Peripheral treatment will resolve abnormalities in vaginal biomarkers evaluated at 8, 16, and 24 weeks, while central treatment will resolve abnormalities in blood biomarkers evaluated at 16 weeks.

All analyses will be performed using the Intent-to-Treat (ITT) population. The ITT population will include all randomized participants. Participants will be grouped according to their randomized allocation, regardless of whether the allocated therapy was administered or switched.

Any deviations from the statistical analyses described above, due to unforeseen circumstances, will be documented in the Statistical Analysis Plan (SAP).

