If the results for question 1a or 1b are statistically significant, the following primary outcomes will be analyzed using the same modeling strategies (models in 1a and 1b above): % decrease in pain score (tampon test) from baseline to the 16-week time point and % decrease in perceived pain on the SF-MPQ from baseline to the 16-week time point. Secondary outcomes include change in mucosal, vulvovaginal muscle, and remote bodily PPTs from baseline to the 16-week time point. Secondary outcomes also include change in pain scores and PPTs from baseline to the 8-week time point and change in pain scores and PPTs from the 16-week to the 24-week time point.

If the result for question 1b is non-significant, we will use the continuous COPC score in model 1b instead of a dichotomous VBD classification to compare treatment success for VBD-p and VBD-c. In addition, we use a binary treatment outcome (achievement of 30% pain reduction) to identify the optimal cutoff of the continuous COPC score in each treatment group.

Secondary analyses of muscle pain based on PPTs will also determine: a) the proportion of women with VBD that have a pelvic muscle pain component; b) differences in the distribution of muscle pain in VBD-p and VBD-c groups; and c) presence of muscle pain to predict treatment outcome. The latter will be tested by including the muscle pain variable (continuous or dichotomous) as part of the fixed effect term in model 1a.

Expected Outcomes. **1)** For women with VBD-p, peripheral lidocaine/estradiol treatment will be more effective than placebo or nortriptyline in reducing numeric pain ratings on the tampon test, perceived pain on the SF-MPQ, and pelvic PPTs on the algometer test at week 8 and week 16. **2)** For women with VBD-c, centrally-targeted nortriptyline treatment will be more effective than placebo or lidocaine/estradiol in reducing numeric pain ratings on the tampon test, perceived pain on the SF-MPQ, and pelvic/remote bodily PPTs on the algometer test at week 16. **3)** For women with VBD-c, combined peripheral and centrally-targeted treatments will be most effective in reducing pain on primary and secondary outcome measures at week 16. **4)** The two VBD subtypes will exhibit differential responses to treatment withdrawal at week 16, such that at the week 24 visit women with VBD-c will exhibit increases in pain after treatment withdrawal compared to women with VBD-p.

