15.6 Sample Size and Power

We are planning to enroll 400 women with VBD, with an estimated attrition rate of 20%. Of note, Reed et al. found that vulvar pain measured on a 0-10 numeric scale has standard deviation 2.0.¹⁰⁴ Salaffi et al¹⁰⁵ noted that 2 points on a 0-10 NRS correspond to a clinically meaningful difference in pain severity. Using these results and assuming the within-subject correlation of 0.5, at a significance level of 0.05, the proposed sample size will provide sufficient power of at least 0.80 to detect differences as small as 0.82 on a 0-10 scale for the overall treatment main effects (3 arms) vs. placebo. To test each individual treatment effect vs. placebo, at a significance level of 0.0167 (Bonferroni-corrected for 3 arms), the proposed sample size can detect differences as small as 0.98 on a 0-10 scale. At a significance level of 0.05, the proposed sample size can detect differences as small as 1.35 and 1.20 on a 0-10 scale for the interaction effect of treatment and each VBD-subtype, given possible splits of 40/60, 50/50, or 60/40 (of note, VBD-p vs VBD-c frequencies were 40/60 at UNC and 50/50 at UCLA clinics in previous studies).

To calculate power for research question IIIa, we used data from our previous study of biomarkers in VBD patients.⁷ Conservatively assuming that VBD-c patients represent 60% (192/320) of the sample and VBD-p patients represent 40% (128/320) of the sample, and adjusting the significance threshold for 4 tier 1 cytokine tests, we will be able to detect mean differences of at least 0.4 SD with the power of 0.84 or greater using a t-test. For IL-8, 0.4 SD translates to approximately 2 pg/mL, and for IL-1ra 0.4 SD translates to 240 pg/mL of the minimal detectable difference. Of note, the mean differences between controls and VBD patients for IL-8 and IL-1ra in our previous study were 4 pg/mL and 300 pg/mL, respectively. Thus, we have sufficient power to detect plausible differences in cytokine levels between the VBD subgroups.

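### Question 3a corrects for 4 tests but poses 8 (four cytokines in each of two sample types), and its model leaves out study site

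*Combined protocol and SAP*

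**What the plan says.** Section 15.4 puts two sets of associations into question 3a. One is an inverse association of the centralness score with "the levels of Tier-1 cytokines in vaginal samples". The other is a positive association with "the levels of Tier-1 cytokines in plasma samples". There are four Tier-1 cytokines (IL-1β, IL-8, IL-17 and IL-1ra), and both lavage and plasma are assayed. Each cytokine level is regressed on the score, and the coefficient is judged by an F-test at a threshold "Bonferroni-corrected for the number of cytokines assessed (4 cytokines corresponding to 4 statistical tests").

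Section 15.6 powers 3a by "adjusting the significance threshold for 4 tier 1 cytokine tests". It takes 192 VBD-c and 128 VBD-p women, a difference of 0.4 SD and a t-test, and reports power of 0.84 or greater.

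On adjustment, the 3a text reads "Covariates will include age and race". The other baseline model, 2a in section 15.3, adjusts for age, race and study site, and model 1a in section 15.2 includes center. Section 15.6 also reports that "VBD-p vs VBD-c frequencies were 40/60 at UNC and 50/50 at UCLA clinics in previous studies".

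**The concern.** The divisor counts cytokines, but the question is asked once per cytokine and sample type, so it is half the number of coefficients that will be tested. A Bonferroni threshold with too small a divisor does not deliver the error rate that it implies. The power figure carries the same miscount. At stake is how far a reported link between subtype and biomarker can be trusted, since 3a is one of the two primary statistical questions of Aim 3.

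The missing site term is a second and independent matter. Samples are collected at two sites. If the mix of women and the measured cytokine level both differ by site, the coefficient for the score picks up part of the site difference.

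**Working it through.** **Inputs.** Four Tier-1 cytokines and two sample types (15.4). Divisor 4, hence 0.05/4 = 0.0125 (15.4, 15.6). Groups of 192 and 128, 0.4 SD, power 0.84 (15.6). Enrollment 400, attrition 20%, hence 320 (15.6).

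**Step 1: reproduce the plan's power.** Noncentrality = 0.4 × √(128 × 192 / 320) = 0.4 × √76.8 = 3.505. The two-sided critical t at 0.0125 on 318 df is 2.512. Power = 0.839, which matches 0.84. So 0.0125 two-sided is the working threshold.

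**Step 2: count the tests.** 4 cytokines × 2 sample types = 8 coefficients. An F-test on a single coefficient is two-sided.

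**Step 3: family-wise error.**
- 4 independent tests at 0.0125: 1 − 0.9875^4 = 4.9%
- 8 independent tests at 0.0125: 1 − 0.9875^8 = 9.6%; bound 8 × 0.0125 = 10.0%
- 8 independent tests at 0.00625: 1 − 0.99375^8 = 4.9%; bound 5.0%

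**Step 4: allow for correlation.** The documents give no correlations, so these are assumed. Multivariate normal statistics were simulated with 400,000 draws per setting. The correlation between sample types was set to zero or to half of that within a sample type.

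| Correlation within sample type | Error, 8 tests at 0.0125 |
|---|---|
| 0.2 | 9.3-9.4% |
| 0.5 | 8.3-8.5% |
| 0.7 | 6.8-7.2% |
| 0.9 | 4.9-5.1% |

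**Step 5: power at the corrected threshold (0.4 SD, 60/40 split, two-sided 0.00625).**
- 192/128: noncentrality 3.505, critical t 2.753, power 0.77
- 240/160: noncentrality 0.4 × √96 = 3.919, critical t 2.749, power 0.88
- About 365-370 usable samples keep 0.84 (0.839 at 365, 0.845 at 370)

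The 400 is relevant because 3a uses baseline samples, which are collected before randomization (sections 10.1 and 10.2). Attrition after randomization does not remove them.

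**Step 6: how much site could matter.** Assume 200 women per site (section 9.2) and the earlier splits. The first site then has 80 VBD-p and 120 VBD-c, and the second has 100 and 100. The second site supplies 100/220 = 45.5% of VBD-c and 100/180 = 55.6% of VBD-p, a gap of 10.1 percentage points. A site shift of s SD in a cytokine biases the subtype contrast by about 0.101 × s. That is 0.02 SD at s = 0.2 and 0.05 SD at s = 0.5. At s = 0.5 the per-test false-positive rate rises from 1.25% to about 2.4%. The size of s is an assumption, because the documents give no site effect.

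**The case against.** The best defense is that the vaginal and plasma hypotheses are separate. They have opposite predicted directions and different biology. As two families of four, each is held at 4.9%. If only results in the predicted direction counted, all 8 tests together would give 1 − 0.99375^8 = 4.9%, because a one-sided test at 0.05/8 has the same critical value as a two-sided test at 0.05/4. This is a legitimate design, but it is not the one written down. Section 15.4 places both sample types in one numbered question with one divisor, says that this divisor equals the number of tests, and names a two-sided test. It does not declare two families or restrict claims by direction. What stands is that 9.6% is close to a ceiling and that declaring two families would be an acceptable remedy.

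On site, section 5.1 standardizes sample collection and processing before screening starts, the splits come from previous studies, and no site difference in cytokines is documented. So site may confound; it is not shown to do so. Omitting site also plays no part in the near-doubling of the error rate, which comes from the test count alone.

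On sample size, using 320 can be read as an allowance for unusable samples. The evidence in section 3.4 that cytokines can be measured in lavage is IL-8 in 7 healthy controls, so 400 usable vaginal samples should not be taken for granted.

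A reader might infer that the same shortfall recurs in questions 1b, 2b and 3b. The documents do not support that, since none of these states a divisor that is too small:
- **1b** has one overall F-test at 0.05. If it is not significant, "we will use the continuous COPC score in model 1b instead of a dichotomous VBD classification" applies, with no threshold given.
- **2b** has three models, with no threshold for the overall test.
- **3b** uses p<0.05 without saying how many models are fitted. The error would be 5% for one joint model, 1 − 0.95^4 = 18.5% for four independent tests and 1 − 0.95^8 = 33.7% for eight.

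These are gaps in specification.

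A reader might also infer that the primary microRNA endpoint is tested without correction. The wording "p-value thresholds kept at 0.05 due to exploratory nature of these analyses" governs Tier 2 and microRNA analyses of subtype association and treatment interaction, which section 15.4 calls secondary. The number of microRNAs to be sequenced is not given, so no count of false positives can be derived.

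**Conclusion.** The test count in 3a is wrong as written: 8 coefficients against a stated 4. The resulting family-wise error is at most 10%, and 9.6% under independence, against an implied 5%. This assumes one family of 8 and two-sided claims. The excess shrinks with correlation and disappears only near 0.9. The plan writes no overall 5% for 3a; it follows from the Bonferroni wording and from the reproduction of 0.84 at 0.0125.

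The omission of site is an inconsistency with models 1a and 2a and a possible source of confounding. With the earlier splits and an assumed shift of 0.5 SD or less, the bias is about 0.05 SD or less.

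All the power figures here, including the plan's 0.84, are proxies. They come from a two-group t-test, whereas the planned test regresses on a score from 0 to 9. The matter concerns a baseline biomarker question and does not touch any treatment comparison.

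**What to change.** 1. In section 15.4, state the 3a family. Either use 0.05/8 = 0.00625, or Holm over the 8 tests, or pre-specify vaginal and plasma as two families of four and say that error is controlled per sample type.
2. Add study site to the 3a covariates, as in 2a.
3. In section 15.6, restate the 3a power for the chosen threshold and the expected number of usable baseline samples, preferably for the regression on the score. If the t-test proxy stays, the figures at 0.00625 are 0.77 (192/128) and 0.88 (240/160).
4. State the number of tests and the threshold for the 1b follow-up comparisons and the 1b fallback, for the 2b overall tests and for 3b.

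The cost is wording and a slightly stricter threshold. No power is lost against the stated 0.84 if about 365-370 baseline samples of each type are usable. With only 320, the loss is from 0.84 to 0.77.
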